### **1. Background and Significance**

Undergoing surgery is a life-altering event, and patients understandably often have severe anxiety prior to and during their surgical procedure. This can poorly impact procedural outcomes not only by causing perioperative hemodynamic instability, but in the case of patients undergoing conscious sedation, impact their ability to comply with perioperative provider instructions. In addition to this, increased preoperative anxiety can result in increased anesthetic requirements in the form of short-acting benzodiazepines and opioids. These pharmacologics not only have short term side effects including respiratory depression and possible apnea but can also in some cases result in addiction and long-term dependence.

Guided meditation is a non-pharmacologic intervention that has proven to be effective in decreasing anxiety. This intervention has recently been adapted to the perioperative area, with several recent trials yielding promising results: meditation not only resulted in decreased perioperative biomarkers of anxiety and stress but also resulted in decreased postoperative pain in the specialties of cardiac and spine surgery. Several guided meditation techniques exist, including the body-scan technique which involves sequentially increasing one's awareness of each body part addressed, as well as breath-focused meditation which involves repeated controlled timed deep inhalations and exhalations – which is in contrast to the physiological effect of anxiety -- rapid and shallow breathing.

Of note, prior and currently ongoing trials have all involved general anesthesia, and none have enrolled patients under conscious sedation. It is worth noting that in vascular surgery, minimally invasive endovascular techniques have overtaken open surgical techniques in the management of Peripheral Vascular Disease (PVD). As these procedures do not require general anesthesia, many providers have moved from the operating room to ambulatory vascular centers or office-based laboratories to perform these procedures under conscious sedation. At the same time, without general anesthesia or paralytics, patients are required to perform tasks such as keeping their extremity still or intermittently holding their breath for extended periods of time. Patients which are unable to completely comply can be subject to repeated imaging attempts, which result in additional doses of contrast administration and ionizing radiation.

Anecdotal data suggests that increased perioperative anxiety increases the likelihood that a patient is unable to hold their extremities still or hold their breath for extended periods of time during the catheterization procedure. By extension, high perioperative anxiety is likely to be associated with increased contrast administration and radiation dose.

We propose to quantify the severity of perioperative anxiety in the form of State Trait Anxiety Inventory (STAI) scores, which we will then address via a guided meditation program that revolves around a body-scan and deep-breathing meditation. We will also collect data regarding Interoceptive Awareness using the Noticing subscale of the Multidimensional Assessment of Interoceptive Awareness (MAIA) score. The ultimate goal of this research is to decrease patient perioperative anxiety and thereby not only improve the perioperative patient experience but also increasing patient intraoperative compliance and thus reducing operative contrast administration and radiation doses.

## 2. Specific Aims and Objectives

We have one specific aim:

1. To test the feasibility and acceptability of a preoperative guided meditation program on patients undergoing vascular surgical procedures for peripheral vascular disease.

## 3. General Description of Study Design

This will be a prospective randomized controlled trial of patients undergoing peripheral vascular interventions. Participants will be randomized to receiving guided meditation during their preoperative history and physical exam versus a standard preoperative history and physical exam on the day of their procedure. Randomization will be performed based on a randomization mobile application.

Schema:

Patient consents to vascular procedure AND consents to trial		Randomize	=>	Intervention group: Guided meditation program preoperatively	=>	Vascular Procedure
	=>					
			=>	Control group: No guided meditation preoperatively (standard of care)	=>	

## 4. Subject Selection

**Inclusion Criteria:** Patients who are >18 years of age who are undergoing an endovascular procedure for a peripheral vascular disease indication with an anesthetic plan for conscious sedation

**Exclusion Criteria:**

Patient related:

1. who have an associated significant psychiatric disorder such as anxiety, panic disorder, depression, psychosis, or bipolar disorder
2. patients who are unable to give informed consent
3. patients who are non-English speaking
4. patients who are pregnant
5. patients with a prior lower extremity amputation
6. patients with chronic sensorimotor deficits of either lower extremity

Procedure related:

1. procedures that are booked as urgent or emergent;
2. procedures that are a combination of an open and endovascular procedure (e.g. an angiogram with a toe amputation)

## **Recruitment Procedures:**

Providers: All vascular surgical attendings and trainees that perform PVIs at Massachusetts General Hospital, Newton Wellesley Hospital, Salem Hospital and Southern New Hampshire Hospital will be notified of this study at an in-person research meeting prior to enrollment of any patients. Should they give verbal consent, they and their patients will be eligible to participate in this study moving forward. The vascular surgery attending will likely be the provider answering the post-procedure provider survey, unless they for some reason are not the attending provider during the procedure; if such is the case, the provider performing the procedure will fill out the post-procedure provider survey- if they had been part of the group that had consented during the in-person research meeting. Otherwise, they will not be requested to fill out the post-provider survey. These will be the same providers that fill out the post-procedural provider questionnaire, which will be completed electronically, in person using an iPad and anticipated to take no longer than 3 minutes to fill out.

Patients: All patients will be personally screened by the vascular surgical attending who they are known to or had been referred to in the case of new patient. This vascular surgical attending will then (1) give approval for his/her patient to be contacted for research purposes, (2) initially introduce the study to the patient AND (3) obtain the patient's permission to be contacted by study staff. Patients will be consented initially either at the preoperative surgical clinic visit or prior to the day of surgery in person if they are inpatient or via telephone if they are not inpatient. If the patients are not inpatient, they will be provided the fact sheet prior to their procedure and intervention on the day of their intervention. Subjects will be given the details about the study and given adequate time to ask questions and talk the study over with family that accompanies them.

The principal investigator or the co-investigators will be responsible for enrolling the patients.

Specific recruitment methods will not be used to enhance recruitment of women or minorities – we aim to enroll a patient population which is representative of the PVD demographic. Members of a minority race and Hispanic patients will be included in this study in a manner exactly the same as white patients and non-Hispanic patients so long as they meet the inclusion criteria. Given that the Massachusetts General Brigham has a large catchment pool, we expect the recruitment pool will adequately reflect the prevalence rates in the community, including proportions of minorities of race or ethnicities.

## **5. Subject Enrollment**

All patients will be screened initially either at the preoperative surgical clinic visit or prior to the day of surgery in person if they are inpatient or via telephone if they are not inpatient. Subjects will be given the

details about the study and given adequate time to ask questions and talk the study over with family that accompanies them.

There will be no separate description for children as they will not be enrolled.

Given that the script for the guided meditation is in English, non-English speakers will not be enrolled.

Given the cognitive requirements to perform meditation, any patient who is unable to provide their own surgical consent will not be enrolled.

The investigators' own patients will be enrolled; however in this situation, a co-investigator will perform the enrollment to minimize the potential for coercion. It will additionally be emphasized that the decision to enroll in the study will not in any other way affect their perioperative clinical care. They will also be advised that they may withdraw from the study at any point at their request.

The post-consent intervention randomization method will be via a randomization application – with block randomization per study site.

## 6. STUDY PROCEDURES

### Study Visits:

Timing	Location	Procedure/Data Collected
At least one day prior to day of vascular intervention: When decision is made to proceed with vascular intervention	Outpatient Clinic vs Inpatient Ward	Screening and consent for enrollment into trial Preoperative Quality of Life survey (PROMIS-10)
Day of vascular intervention: 30 minutes preoperatively, after surgical and anesthesia consents are obtained	Pre-operative holding area	Randomization Pre-meditation STAI-6 if randomized to intervention arm Guided Meditation if randomized to intervention arm Pre- procedural STAI-6 Pre-procedural MAIA (Noticing subscale)
Day of vascular intervention: 2 hours after vascular intervention	Post-anesthesia care unit	Post-procedural Patient Questionnaire Post-procedural Provider Questionnaire Post-procedural MAIA (Noticing subscale)
Outpatient follow-up Typically between two weeks to one month after procedure	Outpatient Clinic	Follow-up Patient Questionnaire Followup Quality of Life survey (PROMIS-10)

**Study Intervention:** A guided meditation using the body scan technique, which will have two sessions- the first session while the patient is in the perioperative holding area and the second session after the patient has been positioned on the operating room table, however this second session will still be completed prior to the beginning of the surgery. This will be administered via a set of Bluetooth headphones (with bone-conduction technology so they do not cover the patients ears), with the associated audio recording being played from an MGB iPad. This protocol, specifically regarding having one session in the perioperative holding area and one session in the operating room was designed by a multidisciplinary panel which included vascular anesthesiologists, perioperative nurses, integrative medicine clinicians and surgeons. this expert panel agreed that the protocol in this form would be most beneficial to the patients and simultaneously cause minimal (if any) disruption to the current operating room workflow.

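### Nothing in the plan keeps allocation from the provider who completes the post-procedure survey, so the provider-rated secondary outcomes are open to expectation bias; the patient-reported primary STAI-6 is not affected by this

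*Combined protocol and SAP*

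**What the plan says.** **The intervention.** Section 6 (Study Intervention) describes two sessions of a recorded body scan. The first is in the holding area. The other is "the second session after the patient has been positioned on the operating room table", and "this second session will still be completed prior to the beginning of the surgery". On delivery it says "This will be administered via a set of Bluetooth headphones", with the recording played from an iPad.

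**The control.** The schema in Section 3 gives controls standard care without meditation. No sham recording or headset is described.

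**The rater.** Section 4 (Recruitment Procedures, Providers) sets the default: "The vascular surgery attending will likely be the provider answering the post-procedure provider survey". If that person was not the attending at the procedure, "the provider performing the procedure will fill out the post-procedure provider survey", provided that this provider had consented at the research meeting. Otherwise no survey is requested.

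**The outcomes.** Section 6 lists as secondary outcomes provider and patient satisfaction, breath-holding, leg immobility, and the extent of additional contrast or radiation. All are taken from a post-procedure questionnaire on a Visual Analogue Scale. The visit table has both a patient and a provider questionnaire two hours after the procedure. The primary outcome is the pre-procedural STAI-6, which the visit table lists under the holding area.

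**Masking.** The documents mention no blinding of the provider, no independent assessor and no rule on who may know the arm. The nearest safeguard is in Section 5: "The investigators' own patients will be enrolled; however in this situation, a co-investigator will perform the enrollment". Its stated purpose is to limit coercion at enrollment.

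**The concern.** A headset on the table, used in one arm only and shortly before the procedure, is a visible sign of allocation in the room where the rater's case is about to start. The raters are not neutral. They are briefed on the study, they introduce it to their own patients, and some may be investigators. What they score is a matter of judgment.

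These ratings carry the later steps of the rationale in Section 1: less anxiety, better compliance during the procedure, and so less contrast and radiation. If the rater knows the arm and expects a benefit, a difference could come from the rating itself, or from patients being coached differently, with no effect of meditation. The pilot is also meant to supply data for powering a later trial (Section 9, Power Analysis), so an inflated difference could carry into that trial's sample size.

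**Working it through.** The plan states no sample size, significance level, effect or SD, so it has no figure to reproduce. The check is first a trace through the text, then an illustration on assumed values.

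**1. Can the rater learn the arm?** The headset and iPad are used on the table in the intervention arm only (Sections 3 and 6). The rater is normally the attending for the case (Section 4). No sentence places the rater in the room during the second session, and none keeps the rater out. Exposure is therefore likely and unprevented, but not established.

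**2. Which outcomes does the rater score?** Provider satisfaction must be on the provider form. Section 6 does not say which of the two questionnaires holds the items on breath-holding, immobility, and contrast or radiation. The provider form is the natural reading.

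**3. Which outcomes lie outside the problem?** The STAI-6 is reported by the patient and is listed under the holding area. The provider's rating does not enter it.

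**4. Could allocation be withheld within the existing procedures?** The visit table puts randomization after surgical and anesthesia consents, so no arm exists during those conversations. The session is a recording, so the rater is not needed to deliver it, and it ends before surgery begins. Nothing in the text requires the rater to know the arm.

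**5. Illustration of size (every input assumed).** Take a 100 mm scale, a rater shift of 5 to 10 mm and a between-patient SD of 20 to 25 mm. The spurious standardized difference is b = shift / SD, from 5/25 = 0.2 to 10/20 = 0.5.

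With n per arm, no true effect and a two-sided 5% t-test, the test statistic follows a noncentral t distribution with 2n − 2 degrees of freedom and noncentrality b × √(n/2). For n = 25 and b = 0.5 this is 0.5 × √12.5 = 1.77. The chance of a false-positive result is then:

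| n per arm | b = 0 | b = 0.2 | b = 0.3 | b = 0.5 |
|---|---|---|---|---|
| 12 | 5.0% | 7.6% | 10.8% | 21.6% |
| 25 | 5.0% | 10.7% | 18.0% | 41.0% |
| 50 | 5.0% | 16.8% | 31.8% | 69.7% |

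The rate rises with n because the shift does not shrink as patients are added. Only b = 0 keeps it at 5%. The table shows how such a bias behaves; it does not estimate the bias in this trial.

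**The case against.** The strongest reply is that this is a feasibility pilot. Its single aim is feasibility and acceptability (Section 2), it has no power analysis, its primary outcome is untouched, and Section 9 names a test for the STAI-6 but none specifically for the Visual Analogue Scale outcomes. That stands as a limit on weight. It does not remove the point, because the ratings will still be compared between arms and may inform a later trial, and a pilot is a good place to learn whether masking works.

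A second reply is that masking cannot be complete, and this also stands. Patients are under conscious sedation and can say what they heard. Section 3 places meditation during the preoperative history and physical, so the first session may be seen. Section 10 has the principal investigator and a collaborator review outcomes after every 25 patients, which could be a further route if either is also a rater and the reviews are by arm; the text settles neither.

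A reader might also infer more than the documents support:

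- *That the rater certainly knows the arm.* No sentence puts the rater at the table during the session.
- *That the rater is always the person who operates.* The attending is the default, the performing provider is the fallback, and trainees also perform these procedures.
- *That every compliance item is provider-rated.* Section 6 does not assign them.
- *That 0.2 to 0.5 SD measures the bias.* It is one assumed number divided by another.
- *That controls must wear a silent headset.* This would alter the standard-care control before compliance, patient satisfaction and the post-procedural MAIA are measured. It is a debatable trade-off and is not asked for here.

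**Conclusion.** The point holds as a gap in the plan. One arm alone has a visible session on the table, a provider involved in the case then gives subjective ratings, and nothing keeps allocation from that provider. Provider satisfaction is exposed for certain to an unmasked-rater design. The ratings of breath-holding, immobility, and extra contrast or radiation are exposed if they sit on the provider form, as is most likely. A favorable difference on these outcomes could not be separated from rater expectation.

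The size is unknown. The illustrative range, from 7.6% (12 per arm, b = 0.2) to 69.7% (50 per arm, b = 0.5) against a nominal 5%, rests wholly on the assumed shift, SD, sample size and test. The STAI-6 comparison is not affected by this rater problem, and the feasibility aim does not depend on it. The change is worth making because it is small, not because the trial fails without it.

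**What to change.** Make three additions by a short amendment:

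1. State in Section 6 that allocation is not disclosed to whoever will complete the provider survey until that survey is submitted. Word the rule for the rater rather than the operator, so that it covers both the default and the fallback in Section 4.
2. Have existing study staff other than that rater randomize, run the iPad for both sessions, and remove the headphones before the rater comes to the table.
3. Add one item to the provider survey asking which arm the provider believes the patient was in, and report the answers by arm beside the provider ratings.

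In the same amendment, say which questionnaire carries the items on breath-holding, immobility, and contrast or radiation.

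The cost is one survey item and some coordination in the room, using staff and equipment already in the trial. The documents give no figures for this, so calling it small is a judgment. The content and timing of the sessions are unchanged. Masking will be partial for the reasons given above. The new item would help show how often it fails, though a correct guess can also reflect a real effect that the provider noticed.

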**Return of Study Results:** The study data will be collected by study staff and electronically converted into a spreadsheet to be stored in LabArchives. The principal investigator will be responsible for managing incidental findings.

**Primary outcome:** Patient pre-procedural anxiety as measured by STAI-6 scores

**Secondary outcome:** Secondary outcomes will include provider and patient satisfaction scores, intraoperative patient ability to perform breath holds and to maintain leg immobility, and the extent to which additional contrast or radiation was required during the procedure. These will be assessed in the form of post-procedure questionnaire and measured on a Visual Analogue Scale.

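### Additional contrast or radiation is measured only by a questionnaire rating, so the pilot will yield no contrast volumes or radiation doses

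*Combined protocol and SAP*

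**What the plan says.** Section 6 (Secondary outcome) names five secondary outcomes: provider satisfaction, patient satisfaction, ability to hold the breath, ability to keep the leg still, and "the extent to which additional contrast or radiation was required during the procedure. These will be assessed in the form of post-procedure questionnaire". The scale for all of them is a VAS. No anchors or range are given, and the text does not say whether the patient or the provider questionnaire carries the contrast and radiation item.

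The Study Visits table in Section 6 lists for the period after the procedure: "Post-procedural Patient Questionnaire Post-procedural Provider Questionnaire Post-procedural MAIA (Noticing subscale"). It has no intraoperative row and no entry for the procedure record.

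Section 1 explains why the outcome is there. Patients who cannot comply may undergo "repeated imaging attempts, which result in additional doses of contrast administration and ionizing radiation", and the ultimate goal includes "increasing patient intraoperative compliance and thus reducing operative contrast administration and radiation doses". Section 8 repeats lower contrast and radiation as a possible benefit for the intervention group and, if the intervention works, for patients more widely.

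The single specific aim in Section 2 is narrower: "To test the feasibility and acceptability of a preoperative guided meditation program". Section 9 (Power Analysis) adds that the pilot should supply preliminary data for powering a later trial.

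**The concern.** Contrast and radiation are physical quantities with units. The plan replaces them with someone's impression, after the procedure, of how much extra was needed. A VAS difference between arms cannot be converted to mL or to a dose unit without recorded values, and none are planned.

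Two things are at stake. First, the pilot would finish with nothing to say about the amounts given in either arm, although lowering them is part of the reason for the research. Section 1 itself calls the evidence linking anxiety to non-compliance anecdotal; a rating adds another perception to that chain. Second, if the later trial takes contrast or dose as an endpoint, its designers would have no mean or SD from this pilot to plan with.

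**Working it through.** The plan gives no figure to reproduce: no sample size, VAS range, mean or SD. The main check is therefore a comparison of the document's own statements.

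1. **Quantity of interest.** Sections 1 and 8 speak of contrast administered and radiation dose.
2. **Measure planned.** Section 6 fixes a questionnaire VAS.
3. **Other possible source.** The visit table lists PROMIS-10, STAI-6, MAIA (Noticing) and three questionnaires whose items are not shown (post-procedural patient, post-procedural provider, follow-up patient). No section mentions contrast volume, dose, fluoroscopy time, repeat runs or abstraction from the procedure record. Because the questionnaire items are not shown, the finding is that none is described. The scale of this outcome, however, is stated.
4. **Analysis.** Section 9 ties its t-test or Mann-Whitney sentence to STAI-6 and names no analysis for recorded procedural values.
5. **Extent.** One of the five secondary outcomes is affected.

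The following arithmetic shows what recorded values would add; it does not measure the defect. Total N is an **assumption**: 25, 50 and 100, split about 1:1, in steps taken from the 25-patient review interval in Section 10, which is not a sample size. With normal data and df = N − 2:

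- Half-width of the 95% CI for a between-arm difference, in SD units = t(0.975, df) × √(1/n₁ + 1/n₂).
- 95% limits for the true SD as multiples of the estimate = √(df/χ²(0.975, df)) to √(df/χ²(0.025, df)).
- Required sample size scales with SD², so its limits are the squares of those multiples.

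| N (arms) | Half-width | SD multiple | Sample-size factor |
|---|---|---|---|
| 25 (12/13) | 2.069 × 0.400 = 0.83 SD | 0.78 to 1.40 | 0.60 to 1.97 |
| 50 (25/25) | 2.011 × 0.283 = 0.57 SD | 0.83 to 1.25 | 0.70 to 1.56 |
| 100 (50/50) | 1.984 × 0.200 = 0.40 SD | 0.88 to 1.16 | 0.77 to 1.35 |

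Adjusting for four sites costs 3 df and gives half-widths of 0.84, 0.57 and 0.40 SD. Recorded values would thus give a planning SD that is rough at N = 25 (1.97/0.60, more than a threefold range in sample size) and better at 50 or 100. At all three sizes the arm comparison is imprecise. The VAS alone gives no SD in these units at any N.

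**The case against.** The strongest reply is that this is a feasibility pilot. Its aim is feasibility and acceptability, its primary outcome is STAI-6, and no aim, primary outcome or planned analysis fails if the VAS is kept. Section 8 speaks of possible and conditional benefits, and Section 9 does not say which endpoint the later trial will be powered on. All of this stands, and it limits the weight of the point.

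The VAS also has a rationale. It asks about *additional* need, which is the step in Section 1 where non-compliance leads to repeated imaging. Total volume and total dose depend on case complexity and do not isolate that step. This stands too. It is a reason to keep the VAS and to add repeat runs where logged, but not a reason to leave the amounts uncollected.

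Values might be pulled from records later. That would be unplanned, might rest on different metrics at different sites, and would have to be squared with the Section 11 limit to data necessary for the study.

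Two stronger readings are tempting:

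- A reader might infer that the trial promises to demonstrate a dose reduction and is bound to fail. The documents make no such promise, and the table above shows that recorded values would not settle the question at these assumed sizes.
- A reader might infer that the ratings are biased because the rater knows the arm. No masking is described, controls receive no meditation, and "The vascular surgery attending will likely be the provider answering the post-procedure provider survey". But which questionnaire carries the item is not stated. The second session ends before surgery begins, and the text does not say that the operator is present for it. Knowledge of allocation is therefore an inference, the size of any bias cannot be computed, and the issue would apply equally to the other VAS outcomes.

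**Conclusion.** The point holds as a limited one. Followed as written, the pilot can report perceived extra need for contrast or radiation but not the amounts, and it supplies no mean or SD in mL or dose units. The second loss matters only if the later trial uses such an endpoint. One of five secondary outcomes is affected. This is an inexpensive improvement the sponsor should make, not a flaw that threatens the pilot's purpose.

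The conclusion rests on the supplied text, in which the questionnaire items are not shown. The cost estimate assumes that the values are routinely logged at the four hospitals named in Section 4 (Recruitment Procedures), which the documents do not confirm.

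**What to change.** - **Section 6 and the visit table.** Add a procedure-record entry with total contrast volume (mL) and one radiation dose metric, named in advance and logged at all sites, plus the number of repeat imaging runs where logged. Abstract them for every randomized patient who has the procedure.
- **Section 9.** State that these values are reported descriptively by arm: mean, SD, median, IQR, and a between-arm difference with 95% CI. Report the percentage of cases in which each value was retrievable, which also informs feasibility.
- **VAS.** Keep it as the measure of perceived additional need. State which questionnaire carries it and who rates it.

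Randomization is planned "with block randomization per study site", but a site-stratified analysis of these values is more than a small pilot needs: 25 patients over four sites and two arms is 25/8, about three per cell.

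**Cost.** An amendment covering the abstraction of record data, and two or three values per case if routinely logged. Totals will still vary with case complexity and will not isolate additional imaging, so the arm comparison should be presented as imprecise. Recorded values remove rating error but not any influence that knowledge of allocation might have on conduct of the procedure.
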